8.6.1 Comparisons Between UX007 and Placebo Groups

Comparisons of primary and secondary endpoints will be performed to test for a difference in the endpoint between UX007 and placebo groups during the double-blind placebo-controlled treatment period. Model based estimates will be presented, with 90% confidence intervals, for each endpoint by treatment group and also for the treatment effect (difference between treatment groups for continuous endpoints and difference between treatment groups for binary endpoints).

Endpoints measured during the double-blind placebo-controlled treatment period only at Week 8 and those measured at both Week 4 and Week 8 will be analyzed differently as described below. Endpoints measured only at Week 8 include those derived from the seizure diary and EEG. Endpoints measured at both Week 4 and Week 8 included those derived from CANTAB, 6MWT and GMFM-88.

Continuous Endpoints:

- Continuous endpoints measured only at Week 8 will be analyzed using linear regression (ANCOVA), with change from baseline to Week 8 as the response variable, treatment group (UX007 vs. placebo) as the primary variable of interest and an appropriate baseline value as an additional covariate.
- Continuous endpoints measured at both Week 4 and Week 8 will be analyzed using generalized estimating equations (GEE), with change from baseline at each timepoint as the response variable; treatment group (UX007 vs. placebo), a factor for visit, visit by treatment interaction and an appropriate baseline value as covariates; identity link function and exchangeable within subject working correlation matrix. The comparison of interest will be based on the LS means difference at Week 8.

Binary Endpoints:

- Categorical (binary) endpoints measured only at Week 8 will be analyzed using logistic regression, with a yes/no indicator as the response variable, treatment group (UX007 vs. placebo) as the primary variable of interest and an appropriate baseline value as an additional covariate.
- Categorical (binary) endpoints measured at both Week 4 and Week 8 will be analyzed using generalized estimating equations (GEE), with a yes/no indicator at each timepoint as the response variable; treatment group (UX007 vs. placebo), a factor for visit, visit by treatment interaction and an appropriate baseline value as covariates; logit link function and exchangeable within subject working correlation matrix. The comparison of interest will be based on the LS means difference at Week 8.

If the number of observations is insufficient for analyses, between group comparisons may not be done and within group tests for no change from baseline may be provided instead.

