4 STUDY ENDPOINTS, COVARIATES AND SUBGROUPS

The clinical efficacy tests / instruments evaluated in this study are summarized in [Table 1](#). See the study protocol for the detailed description of each test.

Table 1: Study Outcomes

Seizure Frequency and Response

- Observable seizures measured by seizure diary [**]
- Absence seizures measured by overnight electroencephalogram (EEG) [**]

Movement

- Movement ability measured by 6-minute Walk Test (6MWT) [*]
- Paroxysmal exertional dyskinesia (PED) events measured by 6MWT [*]
- Gross motor function measured by Gross Motor Function Measure-88 (GMFM 88) [*][#]
- Gait analysis measured during 6MWT [#]

Neurological Function

- Neuropsychological function measured by Computerized Neuropsychological Test - Cambridge Neuropsychological Test Automated Battery (CANTAB) [*]
- Physical neurological findings measured by Columbia Neurological Score (CNS)
- Global impression of disease improvement measured by Clinical Global Impression –Improvement (CGI-I)
- Receptive vocabulary achievement and verbal ability measured by Peabody Picture Vocabulary Test (PPVT) [#]
- Visual and motor coordination measured by Beery-Buktenica Developmental Test of Visual Motor Integration (Beery-VMI) [#]
- Spatial understanding and abstract reasoning measured by Raven’s Coloured Progressive Matrices (RCPM) [#]

Quality of Life

- Physical and psychosocial health-related quality of life measured by Short Form-10 (SF-10) Health Survey in subjects under 18 years of age
- Physical and psychosocial health-related quality of life measured by Short Form-12 (SF-12) Health Survey in subjects 18 years of age and over
- Functional capabilities and performance measured by Pediatric Evaluation of Disability Inventory Computer Adaptive Test (PEDI-CAT)[#]

[**] Primary efficacy measures

[*] Secondary efficacy measures

[#] Measured at select sites only

Each of the primary and secondary endpoints will be compared between the UX007 and placebo groups during the double-blind, placebo-controlled treatment period.

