7 DATA HANDLING AND ACCEPTANCE

7.1 Handling of Missing and Incomplete Data

Missing clinical outcome data can occur for multiple reasons, including missed subject visits and scales or measures with missing item scores. Missing and incomplete data will be identified through a review of tables and listings for this study. Missing and incomplete data will be identified for investigation and possible resolution by Data Management prior to the study database lock.

Unless otherwise specified, for missing assessments for an individual subject, these data would remain as missing. When a change from baseline is assessed, only subjects with a baseline and at least one post baseline measurement will be included in the analysis.

For primary and secondary analyses related to reduction in seizures from baseline to Week 8, imputation will be used to enable inclusion in analyses of all subjects in the Efficacy Analysis Set, the Efficacy Analysis Set – Observable Seizures and the Efficacy Analysis Set – Absence Seizures.

- For observable seizures subjects who have incomplete diary data during the Baseline Period but at least one day complete, observable seizure frequency will be calculated by averaging over the days with complete diary data. The same rule will be used for the Double-Blind Placebo-Controlled Treatment Period. Note that this also applies to subjects who terminate early.
- For absence seizures subjects who have incomplete EEG at either Randomization or Week 8, absence seizure frequency will be calculated by averaging over the time that is complete, even if the EEG is not done overnight.
- For subjects who have completely missing data for either Randomization or Week 8, a reduction from baseline in the natural logarithm of seizure frequency (+ 1) value of zero will be imputed for the response variable in any analyses of reduction from baseline, and non-response will be imputed for the response variable in any analyses of seizure response. For subjects who have completely missing data for Randomization, the Week 8 value will be imputed if available for the baseline covariate; if both Randomization and Week 8 are missing then the average baseline value of the subjects with complete data in the same treatment group will be imputed for the baseline covariate. In additional analyses related to reduction in seizures, two alternate methods will be implemented:

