8.6 Efficacy Analyses

The statistical approach for each efficacy analysis is summarized in [Table 5](#) and will depend on the level of endpoint (primary, secondary, exploratory) and the study periods involved (double-blind placebo-controlled treatment, open-label extension). The statistical approach for Week 8 analyses of primary and secondary endpoints will be comparisons between UX007 and placebo. A more thorough table showing Test/Instrument, Eligible Study Population, Endpoint, Subjects Applicable, Endpoint Level, Timepoints for Assessments, and Statistical Approach by Study Period Analysis is provided in [Appendix A](#). The statistical approach is defined for the following study period analyses:

- Week 8 Analyses: incorporate data up to the end of the double-blind placebo-controlled treatment period
- Week 52 Analyses: incorporate data from the entire study

Each statistical approach is described in the following sections.

Table 5: Efficacy Analyses by Study Period and Endpoint Level

Endpoint Level	Statistical Approach: Week 8 Analyses	Statistical Approach: Week 52 Analyses
Primary and Secondary Endpoints	Comparison Between UX007 and Placebo Groups	Estimation by Treatment Group and Overall
Exploratory Endpoints	Summary Statistics by Treatment Group	Summary Statistics by Treatment Group and Overall
Exploratory Endpoints at Select Sites	Data Listing	Data Listing

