8.6.2 Estimation by Treatment Group and Overall

Estimation by randomized treatment group, for subjects while taking UX007 and overall will be done over time will be analyzed using a generalized estimation equations (GEE) model as follows:

- Continuous endpoints will be analyzed using a GEE linear model, with change from baseline at each timepoint as the response variable; treatment group (UX007 vs. placebo), a factor for visit, visit by treatment interaction and an appropriate baseline value as covariates; identity link function and exchangeable within subject working correlation matrix.
- Categorical (binary) endpoints will be analyzed using a GEE logistic model, with a yes/no indicator at each timepoint as the response variable; treatment group (UX007 vs. placebo), a factor for visit, visit by treatment interaction and an appropriate baseline value as covariates, logit link function and exchangeable within subject working correlation matrix.

All available measurements during the appropriate study period will be included in the model.

If the number of observations is insufficient for analyses, summary statistics will be provided.

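### With about 10 placebo subjects, SAP 8.6.1 lets a within-group test replace the placebo comparison with no threshold, and names no small-sample test for the response and GEE endpoints

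*SAP*

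**What the plan says.** SAP 8.6.1 governs the Week 8 comparisons with placebo.

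- **Two-visit endpoints.** "Continuous endpoints measured at both Week 4 and Week 8 will be analyzed using generalized estimating equations (GEE"). SAP 8.6.4 applies this to eight CANTAB scores, two 6MWT measures and the GMFM-88 total: 8 + 2 + 1 = 11 continuous tests. Link, covariates, working correlation and the Week 8 contrast are fixed. On inference the section says that "Model based estimates will be presented, with 90% confidence intervals, for each endpoint by treatment group and also for the treatment effect". That describes the estimates; it does not settle the variance estimator or the reference distribution.
- **Response endpoints.** "Categorical (binary) endpoints measured only at Week 8 will be analyzed using logistic regression". This covers seizure, observable seizure and absence seizure response. Covariates are given, but no test and no rule for an arm without responders. Onset of PED is a binary GEE.
- **Closing sentence.** If observations are insufficient, "between group comparisons may not be done and within group tests for no change from baseline may be provided instead".

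Elsewhere the SAP commits to the randomised comparison. Section 4: "Each of the primary and secondary endpoints will be compared between the UX007 and placebo groups during the double-blind, placebo-controlled treatment period". Section 8.6: "The statistical approach for Week 8 analyses of primary and secondary endpoints will be comparisons between UX007 and placebo". The parallel rule in 8.6.2 is different: "If the number of observations is insufficient for analyses, summary statistics will be provided". For the Week 8 seizure-reduction analyses, SAP 7.1 says that "imputation will be used to enable inclusion in analyses of all subjects in the Efficacy Analysis Set" and in the sets by seizure type.

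The code in Appendix D is redacted, but the appendix is titled for the primary analysis, so the redaction does not explain gaps in the secondary methods.

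**The concern.** About 40 subjects at 3:1 leaves about 10 on placebo. The CANTAB, 6MWT and GMFM-88 sets can be smaller. Subjects who fail the motor screening test skip the rest of CANTAB, the 6MWT stops if it is not feasible at Screening, and GMFM-88 is done at select sites only (Protocol 7.5.2.2). These are the endpoints for which the closing sentence of 8.6.1 could realistically be used. A test of no change within UX007 credits the drug with any change that would have happened anyway. The practice 6MWT, the Screening CANTAB and a baseline taken as the last value before dosing (SAP 5.1) reduce learning effects but do not rule out drift.

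At this size the unnamed details also matter. The same response data can give very different p-values depending on the test, and an uncorrected GEE standard error can be too small. Secondary endpoints are tested without multiplicity adjustment (Protocol 7.6), so what is at stake is the supportive motor, cognitive and responder evidence.

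**Working it through.** **The plan's own figure.** Inputs from SAP 3.5 and 3.3: difference 50, SD 55, one-sided 0.05, 30 vs 10. Standard error = 55 × √(1/30 + 1/10) = 20.1; 50/20.1 − 1.645 = 0.84; power about 80%, as stated. So 10 placebo subjects is the planned number. It is approximate, because the first three subjects were randomised 1:1.

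**1. Within-group fallback.** Assume no drug effect and a true change of d SDs (SD of the change) in both arms. A one-sided 5% t test in n UX007 subjects rejects with the non-central t probability, non-centrality d√n. The documents give no drift and no subset size, so d and n are assumptions.

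| n | d = 0.1 | d = 0.2 | d = 0.3 |
|---|---|---|---|
| 12 | 9.4% | 16.0% | 25.2% |
| 9 | 8.5% | 13.7% | 20.6% |

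In the between-group test equal drift cancels. At 12:4 its simulated error is 4.2% (Mancl-DeRouen standard error, t reference).

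**2. Response endpoints.** Simulated one-sided error at 30:10, treatment plus two covariates assumed unrelated to response (40,000 trials per rate; 6,000 for score):

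| Null response rate (assumed) | Wald | Likelihood ratio | Firth | Score |
|---|---|---|---|---|
| 18% | 0.2% | 9.7% | 3.0% | 4.3% |
| 23% | 0.7% | 7.8% | 3.7% | 5.1% |
| 29% | 1.9% | 6.8% | 4.2% | 5.0% |
| 50% | 5.0% | 6.1% | 4.8% | 5.6% |

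Wald rejected in none of the trials with 0/10 placebo responders. Example, 15/30 vs 0/10, one-sided p: Wald 0.27 to 0.50 (depending on where the iteration stops), likelihood ratio 0.0004, Firth 0.0015, Fisher C(25,10)/C(40,10) = 0.0039.

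How often might 0/10 occur? Take normal percent reductions with SD 55 and an assumed mean placebo reduction m of 0, 10 or 20. The placebo response rate P(Z > (50 − m)/55) is 0.182, 0.234 or 0.293. Then 0.818^10 = 13%, 0.766^10 = 7% and 0.707^10 = 3%. These are illustrative only: SAP 5.7.3 caps the reduction at 100%, while the normal model puts 18%, 23% or 29% of UX007 subjects (means 50, 60, 70) above that cap.

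Power on the same assumptions (UX007 rates 0.500, 0.572, 0.642): Wald 41%, 52%, 57%; Firth 54%, 58%, 59%; likelihood ratio 61%, 63%, 63%; score 58%, 62%, 64% in a smaller run. A further run gave 59% to 62% for score and 56% to 59% for Firth.

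**3. Continuous GEE.** Simulated one-sided error with no true effect, the five mean terms of 8.6.1, normal data and an assumed correlation of 0.6:

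| Sizes | Sandwich, z | Model-based, z | Mancl-DeRouen, t |
|---|---|---|---|
| 30:10 | 6.7% | 5.1% | 4.4% |
| 15:5 (assumed) | 8.7% | 5.4% | 4.1% |
| 9:3 (assumed) | 12.3% | 6.1% | 4.1% |

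At 30:10 with placebo SD assumed 1.5 times that of UX007: 7.4%, 9.4%, 5.0%. With assumed lognormal data, Mancl-DeRouen with t still gives about 7% to 9% in the upper tail at 30:10.

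**The case against.** The strongest reply is about weight, and much of it stands. These are unadjusted Phase 2 secondary endpoints. At 30:10, the only size the documents support, the GEE excess is under two points for the sandwich and close to nil for model-based errors when SDs are equal. The smaller subsets, unequal SDs and drifts are all assumed.

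The fallback sentence is permissive and labels its output plainly as tests of change from baseline. A reader might infer that the sponsor intends to present an uncontrolled change as efficacy against placebo; nothing in the documents says so. The 8.6.2 rule has no threshold either.

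A reader might also infer that leaving the response test open means choosing between a test that cannot reject and one that rejects too often. That does not hold: the score test is an ordinary third option with error of about 4% to 6%, and Firth is another. Nor does the case for Mancl-DeRouen rest on the planned size with equal SDs, where model-based errors with a t reference also do well; it rests on the possibility of unequal SDs.

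None of this supplies the missing threshold, the missing test or the missing standard error, and none of it reconciles the closing sentence of 8.6.1 with Sections 4 and 8.6.

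**Conclusion.** The concern holds in three parts of unequal weight.

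1. **Main.** The permission to substitute a within-group test, with no threshold, conflicts with the comparisons promised in Sections 4 and 8.6. Its size depends on the assumed drift and subset.
2. **Real.** No test is named for the three response endpoints, and the candidates disagree sharply when placebo responders are few or absent. The binary PED GEE has the same problem if no UX007 subject has PED, which would be the favourable result; SAP 8.6.4 itself expects PED onset to be uncommon.
3. **Minor at planned size.** No GEE standard error or reference distribution is named; this matters more in small subsets or with unequal SDs.

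A reader might infer that the primary result is at risk. The documents do not support that. Points 2 and 3 do not touch the primary ANCOVA or the two seizure-reduction ANCOVAs. The closing sentence of 8.6.1 formally sits in the section that the primary analysis uses, but the imputation in SAP 7.1 brings every subject in the Efficacy Analysis Set into that analysis, so too few observations is not a realistic trigger there.

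**What to change.** Amend SAP 8.6.1 before Week 8 unblinding:

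1. Replace the closing sentence with the 8.6.2 rule and a stated minimum per arm. Below it, show summary statistics by arm, with no within-group test in place of the comparison. Five per arm is one example: at 15:5 the corrected 90% interval is already about 1.6 SD wide, against 2.4 SD at 9:3. By-arm summaries are already planned in 8.6.4, so this adds no output.
2. Prespecify one test for the response endpoints that works with an empty cell: the score test, or Firth penalised likelihood where an estimate and 90% interval are also needed, with Fisher's exact test as a check. State an equivalent rule for PED. Firth costs about 3 to 4 points of power against the score test.
3. Prespecify a small-sample GEE standard error with a t reference, for example Mancl-DeRouen with subjects minus 5 degrees of freedom. State that it does not fully correct strongly skewed scores, possibly including reaction times.

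The cost of item 3 at 30:10 is intervals 14% wider than sandwich with z (1.035/0.907 = 1.14) and 7% wider than model-based (1.035/0.964 = 1.07). Power at an assumed 0.8 SD effect is 82%, against 87% and 86%. At an assumed 15:5 it is 51%, against 68% and 61%, part of that gap being excess error in the uncorrected tests. Otherwise the change is SAP wording and a little code.

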8.6.2 Estimation by Treatment Group and Overall

Estimation by randomized treatment group, for subjects while taking UX007 and overall will be done over time will be analyzed using a generalized estimation equations (GEE) model as follows:

- Continuous endpoints will be analyzed using a GEE linear model, with change from baseline at each timepoint as the response variable; treatment group (UX007 vs. placebo), a factor for visit, visit by treatment interaction and an appropriate baseline value as covariates; identity link function and exchangeable within subject working correlation matrix.
- Categorical (binary) endpoints will be analyzed using a GEE logistic model, with a yes/no indicator at each timepoint as the response variable; treatment group (UX007 vs. placebo), a factor for visit, visit by treatment interaction and an appropriate baseline value as covariates, logit link function and exchangeable within subject working correlation matrix.

All available measurements during the appropriate study period will be included in the model.

If the number of observations is insufficient for analyses, summary statistics will be provided.

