2.2 Secondary Objectives

The secondary objectives of the study are to:

- Evaluate the efficacy of UX007 compared to placebo, as measured by:
 - Seizure response at Week 8, defined as at least 50% reduction from baseline to week 8 in frequency of seizures
 - Change from baseline to Week 8 in cognitive function using the Cambridge Neuropsychological Test Automated Battery (CANTAB)
 - Change from baseline to Week 8 in distance walked as measured by 6MWT
 - Time to onset of paroxysmal exertional dyskinesia (PED) as measured during 6MWT from baseline to Week 8
 - Change from baseline to Week 8 in gross motor function using the Gross Motor Function Measure-88 (GMFM-88) (assessed at select sites)
- Evaluate long-term efficacy as measured by changes from baseline in frequency of seizures over time
- Evaluate the optimal dose to control seizures and impact on other clinical manifestations during the Dose Exploration Period

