4.2 Secondary Efficacy Endpoints

The following are considered secondary endpoints to evaluate the efficacy of UX007 in Glut1 DS:

- Reduction from baseline to week 8 in frequency of observable seizures (normalized to a 4-week rate) measured for 6 weeks after 2-week titration by diary
- Reduction from baseline to week 8 in frequency of absence seizures (normalized to a 4-week rate) measured overnight by EEG
- Seizure response at Week 8, defined as at least 50% reduction from baseline to week 8 in frequency of seizures
- Observable seizure response at Week 8, defined as at least 50% reduction from baseline to week 8 in frequency of observable seizures measured by diary
- Absence seizure response at Week 8, defined as at least 50% reduction from baseline to week 8 in frequency of absence seizures measured overnight by EEG
- Cognitive function using the Cambridge Neuropsychological Test Automated Battery (CANTAB): change from baseline to Week 8 in the following scores:
 - Reaction Time (RTI):
 - Simple Choice Median Reaction Time (RTIMDSRT)
 - Five Choice Median Reaction Time (RTIMDFRT)
 - Simple Choice Standard Deviation (RTISRTSD)
 - Spatial Span (SSP):
 - Span Length (SSPSLF)
 - Paired Associates Learning (PAL):
 - Total Errors (Adjusted) (PALTEA)
 - First Trial Memory Score (PALFTMS)

- Spatial Working Memory (SWM):
 - Between Errors (SWMBE48)
 - Strategy (SWMS68)
- Change from baseline to Week 8 in distance traveled (in meters) as measured by 6MWT
- Change from baseline to Week 8 in distance traveled (in percent predicted) as measured by 6MWT
- Time (in minutes) to onset of paroxysmal exertional dyskinesia (PED) as measured during 6MWT through Week 8
- Gross motor function using the Gross Motor Function Measure-88 (GMFM-88): change from baseline to Week 8 in Total Score.
- Reduction from baseline over time in frequency of seizures (normalized to a 4-week rate): observable seizures measured daily by diary and absence seizures measured overnight by electroencephalography (EEG)
- Reduction from baseline over time in frequency of observable seizures (normalized to a 4-week rate) measured daily by diary
- Reduction from baseline over time in frequency of absence seizures (normalized to a 4-week rate) measured overnight by EEG

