5.5 Change from Baseline and Percent Change from Baseline

Generally, for measurements at any timepoint T after baseline, change from baseline is defined as

$$\text{Change from Baseline at } T = \text{Measurement at } T - \text{Measurement at Baseline}$$

Percent change from baseline at T is defined as

$$\begin{aligned} \text{Percent Change from Baseline at } T \\ = 100 \times \frac{\text{Measurement at } T - \text{Measurement at Baseline}}{\text{Measurement at Baseline}} \end{aligned}$$

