8.6.3 Primary Efficacy Endpoint

The primary efficacy endpoint is the reduction from baseline to week 8 in frequency of seizures (normalized to a 4-week rate): observable seizures measured for 6 weeks after 2-week titration by diary and absence seizures measured overnight by electroencephalography (EEG). Observable seizure frequency at baseline will be calculated based on approximately 6 weeks between the screening and randomization visits and observable seizure frequency at week 8 will be calculated based on approximately 6 weeks between the end of titration and the week 8 visit (see Section 5.7.1). Absence seizure frequency will be based on overnight EEG at the randomization and week 8 visits.

The primary efficacy endpoint will be derived for each subject based on subject seizure type at randomization: observable seizures from the diary will be used for Observable Seizures Subjects and absence seizures from EEG will be used for Absence Seizures Only Subjects (see Section 5.6).

The primary efficacy endpoint will be analyzed, based on the Efficacy Analysis Set, using a linear regression (ANCOVA) model as described for continuous endpoints in Section 8.6.1. Logarithmic transformations will be used for modeling. The response variable in the model will be the reduction in the natural logarithm of the seizure frequency (+ 1) from baseline to Week 8 and the baseline covariate will be the natural logarithm of the baseline seizure frequency (+ 1): observable seizures from the diary will be used for Observable Seizures Subjects and absence seizures from EEG will be used for Absence Seizures Only Subjects.

An additional covariate will be included that indicates whether the subject is an Observable Seizures Subject or an Absence Seizures Only Subject. Estimates and 90% confidence intervals of percent reduction in seizure frequency will be derived from the model for each treatment group and for the difference between groups.

Missing data will be imputed as specified in Section 7.1. Sensitivity analysis assessing the impact of missing data will be performed using the methods described in Section 7.1.

Percent reduction from baseline in frequency of seizures over the entire study period will be summarized by visit (see Section 5.7.1), and by treatment group, for subjects while taking UX007, and overall.

The following additional analyses will be performed:

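### SAP 8.6.2 does not carry the Week 8 log scale or seizure-type indicator into the Week 52 seizure-frequency model; read literally, that model is on raw change

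*SAP*

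**What the plan says.** Long-term seizure control is a secondary objective (SAP 2.2): "Evaluate long-term efficacy as measured by changes from baseline in frequency of seizures over time". SAP 4.2 lists three matching endpoints (all seizures, observable, absence). The pooled one reads "Reduction from baseline over time in frequency of seizures (normalized to a 4-week rate".

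Table 5 in SAP 8.6 assigns the Week 52 analyses of primary and secondary endpoints to "Estimation by Treatment Group and Overall", which is section 8.6.2. Appendix A repeats this for each seizure endpoint. The continuous model in 8.6.2 is: "Continuous endpoints will be analyzed using a GEE linear model, with change from baseline at each timepoint as the response variable". Its covariates are "treatment group (UX007 vs. placebo), a factor for visit, visit by treatment interaction and an appropriate baseline value as covariates". The link is identity and the working correlation exchangeable. SAP 5.5 supplies the meaning of change: "Generally, for measurements at any timepoint T after baseline, change from baseline is defined as" the value at T minus the value at baseline.

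For Week 8 the plan says more. SAP 8.6.3 makes the response the "reduction in the natural logarithm of the seizure frequency (+ 1) from baseline to Week 8", takes the log of the baseline too, and adds: "An additional covariate will be included that indicates whether the subject is an Observable Seizures Subject or an Absence Seizures Only Subject". SAP 8.6.4 puts the separate observable and absence frequency models on the log scale and gives the pooled response model the indicator, all for comparisons up to Week 8.

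**The concern.** The sponsor judged at Week 8 that seizure counts need a log scale and that the pooled endpoint needs a term separating diary-scored from EEG-scored subjects. The same variables are modelled again over a year, in a section that states neither. An analyst following 8.6.2 and 5.5 would average raw changes.

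Three things follow. The long-term estimate is an arithmetic change, whereas the Week 8 result is a percent reduction from a log model. A subject with many seizures counts for much more than one with few. In the pooled model, diary rates per 28 days (5.7.1) and EEG rates per 24 hours (5.7.2) enter one average, although 4.2 labels both as 4-week rates. An analyst who does not follow the text literally must choose scale and covariates, and SAP 3.6 places the final analysis after the Week 8 analysis. That choice could therefore be made with Week 8 results in hand.

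**Working it through.** **The plan's own figure.** The plan gives no figure for the Week 52 analysis. Its only design figure is power of about 80% for a 50-point difference, SD 55, about 40 completers and one-sided 0.05. With 30 and 10 subjects: 50 / (55 × √(1/10 + 1/30)) = 2.49; 2.49 − 1.645 = 0.845; power 80.1% (78.8% by noncentral t). It reproduces, and this point does not depend on it.

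**Does any other text supply the scale or the indicator for Week 52?**
- SAP 8.6.3 and 8.6.4 add the log and the indicator to the models of 8.6.1, for change to Week 8. Nothing similar is added to 8.6.2.
- SAP 8.1 says how a log of seizure frequency is taken (natural log, add 1), not which models use it.
- SAP 4.5 permits the indicator but does not require it. Its sentence on transformations covers covariates, not the response.
- Appendix D is redacted and titled for the primary analysis, so nothing is inferred from it.

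**Two subjects, using the documents' own range.** Protocol 7.4.3 describes some patients with daily seizures and others with seizures weeks or months apart; the observable-seizure entry minimum is 2 per 4 weeks. Let both halve.
- Raw: 28 to 14 contributes 14; 2 to 1 contributes 1. Ratio 14.
- ln(+1): ln(29/15) = 0.66; ln(3/2) = 0.41. Ratio 1.6.

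**Forty diary subjects.** Assumed, since no distribution is documented: baseline median 8 per 4 weeks with a floor of 2, everyone halved, 4,000 simulations per setting. Median share of the summed change from the 4 highest subjects (10% of the sample):

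| SD of log baseline | Raw | ln(+1) |
|---|---|---|
| 0.8 | 30% | 12% |
| 1.2 | 42% | 12% |
| 1.6 | 54% | 12% |

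**Pooled endpoint at a visit with EEG.** Assumed: n of 40 subjects scored by EEG at baseline E per 24 h, the rest at 8 per 4 weeks by diary, all halved. Raw EEG share = n(E/2) / [n(E/2) + (40 − n)(8/2)]; with E × 28 in place of E if converted to 4 weeks.

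| n | E per 24 h | Head count | Raw, 24-hour unit | Raw, 4-week unit | ln(+1), 24-hour / 4-week |
|---|---|---|---|---|---|
| 5 | 5 | 12.5% | 12.5/152.5 = 8% | 350/490 = 71% | 12% / 14% |
| 10 | 20 | 25% | 100/220 = 45% | 2,800/2,920 = 96% | 27% / 28% |
| 15 | 60 | 37.5% | 450/550 = 82% | 12,600/12,700 = 99% | 41% / 41% |

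The log-scale share stays near head count whichever unit is used. The raw share does not.

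**Fitted model.** An exchangeable GEE with the 8.6.2 terms was simulated 150 times per setting in a deliberately contrasting case: 10 of 40 subjects EEG-scored (median 20 per 24 h) and halving, diary subjects unchanged, log SD 0.8 or 1.2, either EEG unit. Dropping the 4 highest-baseline subjects left a median 14% to 36% of the raw Week 26 estimate. With ln(+1) and the indicator, 65% to 81% remained.

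**Which visits.** Overnight EEG is scheduled at Weeks 0, 8, 26 and 31. Absence Seizures Only subjects, who are scored by EEG, therefore have no pooled-endpoint data at Weeks 14, 36, 44 or 52, and SAP 7.1 rules out imputation in the open-label period.

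**The case against.** The strongest reply is that 8.6.2 is a generic template and never says raw. SAP 8.6.1 is just as generic, 5.5 is qualified as a general rule, and the scale for Week 8 comes from the endpoint section. A sensible statistician would probably carry the log forward. That stands as far as intent goes: the accurate statement is that the Week 52 scale is not specified and the default definition is a plain difference. It does not fill the gap, because 8.6.3 ties its response to Week 8.

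Several stronger readings are tempting, and the documents do not support them.
- *The raw-scale interval would be very wide.* Take 30 diary subjects (median 12 per 4 weeks), 10 EEG-scored (median 40 per 24 h), log SD 0.8 to 1.2 and everyone halved. An unadjusted mean change then has a 90% half-width of 34% to 45% of the estimate on the 24-hour unit. But 8.6.2 includes a baseline covariate. With it, fits under slightly different noise settings gave 14% to 26% raw against 16% to 24% log. Only on the 4-week EEG unit was raw clearly worse in the full model: 23% to 36% against 18% to 26%.
- *Week 8 and Week 52 could not be compared.* The Week 52 analysis uses data from the whole study with a visit factor, so Week 8 and later visits share one model and one scale. By-visit percent-reduction summaries (8.6.3) and Week 52 estimation of the 50% response (Appendix A) are also planned.
- *EEG-scored subjects determine the Week 52 value.* They have no EEG after Week 31. Any later effect is indirect, through the shared baseline coefficient.
- *A few subjects will set the estimate.* At low EEG counts on the 24-hour unit, the EEG share is below head count (8% against 12.5%).

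Mixing of diary and EEG rates concerns only the pooled endpoint. The separate observable and absence endpoints avoid it, though not the influence of high counts.

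**Conclusion.** The point holds as a gap in specification with a real consequence if the text is followed. SAP 8.6.2 with 5.5 gives a raw-difference model for long-term seizure frequency, without the log scale or indicator used at Week 8. High-frequency subjects can then dominate all three long-term frequency endpoints, and diary and EEG rates are combined in the pooled one at Weeks 8, 26 and 31.

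The size cannot be fixed from the documents. Under the stated assumptions, the top 10% of diary subjects carry 30% to 54% of the raw change against about 12% on the log scale. The EEG-scored share runs from 8% to 82% on the 24-hour unit and 71% to 99% on the 4-week unit, against 12% to 41% on the log scale. The upper figures owe much to the conflict of units between 4.1/4.2 and 5.7.2.

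This is secondary, long-term estimation in a Phase 2 trial. The Week 8 primary test is untouched. The change should still be made, because it removes a choice that could otherwise follow the Week 8 results.

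**What to change.** Add to SAP 8.6.2:
- For seizure-frequency endpoints, the response is the reduction in ln(frequency+1) and the baseline covariate is ln(baseline frequency+1).
- The pooled endpoint also includes the Absence Seizures Only indicator.
- Visit estimates are back-transformed to percent reduction as at Week 8.

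Alongside this, reconcile the EEG unit (4-week in 4.1 and 4.2, 24-hour in 5.7.2). State that pooled estimates after Week 31, and at Week 14, rest on observations from diary-scored subjects only.

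The cost is a few sentences in the SAP. No new data, visits or site procedures are needed.
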